3.1.2 Part B (Therapy at 1 and/or 3 mg/kg)

Subjects who meet qualifying criteria may commence Part B (Therapy at 1 and/or 3 mg/kg) after completing Part A, and after the SRC and Sponsor have evaluated an individual subject's available safety data and has deemed it acceptable for that subject to initiate continued therapy in Part B. Only subjects who meet eligibility criteria for Part B will re-initiate SBC-103 dosing in Part B. Refer to Section 4.3.3. Eligible subjects may re-initiate SBC-103 dosing in Part B no sooner than 4 weeks after the subject's last dose in Part A.

In Part B, dose or dosing frequency (eg, QOW or QW) modifications may be considered by the Sponsor after consultation with the SRC, based on a review of safety, tolerability and treatment response data. With the intent of treating patients with the lowest dose that is safe and tolerable and which has potential for efficacy, dose modification (either an increase to 1 or 3 mg/kg, or a decrease to 0.3 or 1 mg/kg) may be proposed for individual subject(s) after evaluation of the safety and tolerability data as well as biomarker and treatment response data after 24 weeks of study participation.

Dose modifications will not be considered until Part B of the study, except for instances where a dose reduction is required for reasons of safety and tolerability. Subjects who receive doses of 0.3 mg/kg in Part A may be considered for a second dose escalation to 3 mg/kg at any time during Part B provided that they have tolerated at least 2 doses of 1 mg/kg in Part B.

Details regarding the maximum planned dose to be evaluated, dose adjustments, and stopping rules in the event of poor tolerability are provided in Section 6.1 and Section 6.2.

Safety, PK, and PD/efficacy assessments will be conducted at regular intervals throughout Part B as specified in the SOA for Part B. See Sections 14.2 and 14.3 (Appendix B and Appendix C).

Subjects who have received and tolerated at least 4 doses of SBC-103 QOW at 3 mg/kg may be considered for participation in Part C (see Section 3.1.3 and Section 4.3.4). Subjects will continue to be dosed in Part B of the study until necessary regulatory and ethics committee review and approval (where required) are obtained for each site to dose escalate in Part C. Subjects who are unable to tolerate at least 4 doses of SBC-103 at 3 mg/kg will continue to be dosed at the highest tolerable dose in Part B until study completion.

If a subject prematurely discontinues, a follow-up call will be made 4 weeks after the subject's last administered dose in Part B unless the subject has a scheduled follow-up visit.

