The decision to continue dosing in the 1st subject in the 1 st , 2 nd , and 3 rd cohorts will be made by the Sponsor based on SRC recommendations after review of 24-hour safety data from that subject and available safety data from all other subjects.
The decision to initiate dosing in the 2nd subject of each cohort will be made by the Sponsor based on SRC recommendations after review of 24-hour safety data from Subject 1 in the same cohort and available safety data from all other subjects.
The decision to initiate dosing in the 3rd subject of each cohort will be made by the Sponsor based on 24-hour safety data from Subject 2 in the same cohort and available safety data from all other subjects.
The decision to escalate into the next dose cohort will be made by the Sponsor based on SRC recommendations after review of safety data from the 1 st subject who completes the first 4 doses in the dose cohort, 24-hour safety data after the first dose from the 3 rd subject of the same cohort, and available safety data from all other subjects.
Part B (Therapy at 1 and/or 3 mg/kg):
Subjects who meet qualifying criteria may commence Part B (Therapy at 1 and/or 3 mg/kg) after completing Part A, after the SRC and Sponsor have evaluated an individual subject's available safety data, and deemed it acceptable for that subject to initiate continued therapy in Part B. Only subjects who meet eligibility criteria for Part B will re-initiate SBC-103 dosing in Part B. Eligible subjects may re-initiate SBC-103 dosing in Part B no sooner than 4 weeks after

the subject's last dose in Part A.
In Part B, dose or dosing frequency (eg, QOW or weekly) modifications may be considered by the Sponsor after consultation with the SRC, based a review of safety, tolerability, and treatment response data.

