1.3 Nonclinical Data

In vitro studies with SBC-103 using NAGLU-deficient human fibroblasts have demonstrated efficient mannose-6 phosphate dependent cellular uptake with correction of intracellular enzyme deficiency. In addition, mannose receptor-mediated uptake of SBC-103 by cells of macrophage lineage has also been demonstrated.

Several nonclinical studies demonstrated a reduction in total HS in NAGLU-deficient mice following IV administration of SBC-103 (4-6 repeated doses), with doses ranging from 0.3 to 27 mg/kg for up to 6 weeks in duration. The results demonstrated dose-dependency. Reductions in HS concentrations were accompanied by increases in measured NAGLU concentration. Following SBC-103 administration, clinical signs such as lethargy and ataxia were observed. The majority of the observations occurred after the third or fourth dose. These observations were not considered to be directly related to pharmacological effect of SBC-103. In these studies, hypersensitivity reactions, which were sometimes fatal, were attributed to the repeat IV administration of a human recombinant protein to a heterologous species (SBC103-P004, SBC103-P007, SBC103-P009, SBC103-P010) and are consistent with published literature (Hovland 2007, Toxicol Pathol; Flaherty 2012, Toxicological Sciences; Finkelman 2007, J Allergy Clin Immunol; Khodoun 2011, PNAS). Pretreatment with diphenhydramine was used to minimize the effects, but did not completely block the reactions. This finding is consistent with the existence of 2 distinct pathways of anaphylaxis in mice; either by Immunoglobulin E (IgE) mediated histamine release from mast cells or by Immunoglobulin G (IgG) mediated PAF release from macrophages (Finkelman 2007, J Allergy Clin Immunol).

In the study SBC103-P010, the potential for CNS uptake and activity following IV administration of SBC-103 was evaluated in NAGLU-deficient mice. These mice were administered 0.3, 1, 3, 5 or 10 mg/kg of SBC-103 once every week (QW) for 4 weeks. A statistically significant decrease in HS was demonstrated in both brain and liver following IV dosing with a pharmacologically active dose (PAD; the lowest dose tested with the intended pharmacologic activity) established at a dose level of 3 mg/kg (0.075 mg dose for a 25 gram mouse) IV in the brain and 0.3 mg/kg (0.0075 mg dose) in the liver (SBC103-P010).

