4.3.4 Qualifications for Participation in Part C (Therapy at 5 and/or 10 mg/kg)

Subjects are eligible for continued SBC-103 dosing at a higher dose (5 or 10 mg/kg QOW) in Part C if they do not meet any Exclusion criteria listed above and if they:

- 1. Have completed at least 4 doses of 3 mg/kg in either Part A or Part B with no unmanageable study drug toxicity; and
- 2. Continue to meet Section 4.3.1 Inclusion Criteria items 4-7.

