Structural and Diffusion MRI ⁸													X ^P							

14.2 Appendix B: Schedule of Study Assessments (Part B, Therapy at 1 and/or 3 mg/kg – Year 1)

Page 103 of 121

	Schedule of Study Assessments												
		Part B: Therapy at 1 and/or 3 mg/kg (Weeks 28 through 52)											
Assessments	Week 28	28 Week 30 Week 32 Week 34 Week 36 Week 38 Week 40 Week 42 Week 44 Week 46 Week 48 Week 50 Week 52											
Visit Window (Days)*	+3	±5	±5	±5	±5	±5	±5	±5	±5	±5	±5	±5	±5
SBC-103 Dosing	Х	Х	Х	Х	Х	Х	Х	Х	Х	Х	Х	Х	Х
Adverse Events ¹⁰						С	ONTINUOU	S					
Concomitant Medications ¹¹						С	ONTINUOU	S					

Key: ADA = anti-drug antibodies; BOT-2 Brief Form = Bruininks-Oseretsky Test of Motor Proficiency, Second Edition, Brief Form; BSID-III = Bayley Scales of Infant and Toddler Development, Third Edition; CCC-2 = Children's Communication Checklist, Second Edition; CSF = cerebrospinal fluid; CSHQ = Children's Sleep Habits Questionnaire; ECG = electrocardiogram; FDNA = Facial Dysmorphology Novel Analysis; HGF = hepatocyte growth factor; IgG = immunoglobulin G; KABC-II = Kaufman Assessment Battery for Children, Second Edition; NAGLU = alpha-Nacetylglucosaminidase; NRE = non-reducing end; SBRS = Sanfilippo Behavior Rating Scale; SF-10 = 10-item Short Form Health Survey for Children; Vineland-II = Vineland Adaptive Behavior Scales, Second Edition; ZBI = Zarit Burden Interview, 12-item.

* All study visits will be scheduled relative to Day 0; infusions must be administered at least 10 days apart.

X^P Assessments to be performed pre-dose.

1. Vital signs will be taken pre-dose (within approximately 30 minutes), approximately every 15 minutes during infusion and approximately every 15 minutes for 2 hours after completion of the infusion. Vital signs will be obtained after any lumbar puncture as per site standard of care.

- 2. The Vineland-II, BSID-III or KABC-II, BOT-2 Brief Form, and CCC-2 should be administered in-person by an appropriately qualified professional.

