Adverse Events ¹¹							CONTINUO	US						
Concomitant Medications ¹²							CONTINUO	US						

Key: ADA = anti-drug antibodies; BOT-2 Brief Form = Bruininks-Oseretsky Test of Motor Proficiency, Second Edition, Brief Form; BSID-III = Bayley Scales of Infant and Toddler Development, Third Edition; CCC-2 = Children's Communication Checklist, Second Edition; CSF = cerebrospinal fluid; CSHQ = Children's Sleep Habits Questionnaire; D = day; ECG = electrocardiogram; FDNA = Facial Dysmorphology Novel Analysis; HGF = hepatocyte growth factor; IgG = immunoglobulin G; KABC-II = Kaufman Assessment Battery for Children, Second Edition; NAGLU = alpha-Nacetylglucosaminidase; NRE = non-reducing end; SBRS = Sanfilippo Behavior Rating Scale; SF-10 = 10-item Short Form Health Survey for Children; Vineland-II = Vineland Adaptive Behavior Scales, Second Edition; Wk = week; ZBI = Zarit Burden Interview, 12-item.

* All study visits will be scheduled relative to Day 0; Infusions must be administered at least 10 days apart.

X^P Assessments to be performed pre-dose.

- 1. Vital signs will be taken pre-dose (within approximately 30 minutes), approximately every 15 minutes during infusion and approximately every 15 minutes for 2 hours after completion of the infusion. Vital signs will be obtained after any lumbar puncture as per site standard of care.
- 2. The Vineland-II, BSID-III or KABC-II, BOT-2 Brief Form, and CCC-2 should be administered in-person by an appropriately qualified professional.
- 3. The coagulation laboratory panel should be collected within 48 hours prior to performing the lumbar puncture, and the results should be available prior to sedating/anesthetizing the subject or performing the lumbar puncture. The procedure (including the initiation of sedation/anesthesia) will not commence until the site receives these results and confirms that it is safe for the subject to receive anesthesia/sedation and the lumbar puncture. To facilitate this process, all coagulation panels (as of 23 March 2015) will be drawn and analyzed locally rather than sent to the central laboratory for analysis.
- 4. Central lab reference ranges will be used throughout the study, including in the event that labs are analyzed locally. All attempts should be made to draw lab samples for central lab analysis when samples are needed for local analysis.
- 5. If a urine sample is not able to be provided, a serum pregnancy test will be performed by a local laboratory.

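### The protocol names weekly dosing as a possible Part B change, but the Part B schedules set a 10-day minimum between infusions without exception; the two need reconciling.

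*Protocol*

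**What the plan says.** **Frequency in Part B.** Protocol Section 3.1.2 states that "dose or dosing frequency (eg, QOW or QW) modifications may be considered by the Sponsor". The synopsis repeats this under Methodology ("dose or dosing frequency (eg, QOW or weekly) modifications may be considered by the Sponsor after consultation with the SRC") and again under the Part B dosing schedule. Section 1.3 defines QW as weekly and QOW as every other week.

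**Minimum interval.** The footnote to the Part B Year 1 schedule (Appendix B) reads "All study visits will be scheduled relative to Day 0; infusions must be administered at least 10 days apart". Both Part B tables for Years 2 and 3 (Appendix C) carry the same rule. SAP Sections 9.1.2 and 9.1.3 reproduce all three tables with the footnote intact. None of them exempts weekly dosing. Dosing columns run at two-week steps: 28, 30, 32 and so on.

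**Where the interval rule is absent.** Section 6.1 states the 10-day minimum in its Part A and Part C paragraphs. Its Part B paragraph limits only the gap between the last Part A dose and the first Part B dose. The synopsis follows the same pattern: the rule appears in the Part A and Part C dosing schedules, not in the Part B one.

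**Entry to Part C.** Section 3.1.2 and the synopsis Methodology ask for at least four tolerated doses of 3 mg/kg given every other week. Section 4.3.4, and the matching synopsis list, omit the frequency: "Have completed at least 4 doses of 3 mg/kg in either Part A or Part B".

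**The concern.** The protocol names a regimen as an available modification, and its own schedule footnotes rule that regimen out. If the Sponsor approved weekly dosing for a child, the site would hold an approved instruction and a mandatory interval that cannot both be kept. Every second infusion would also have no column in the schedule, so the assessments due at that infusion would have to be inferred.

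The silence of Section 6.1 on Part B makes it worse. A reader cannot tell whether the 10-day rule was deliberately left out there to make room for weekly dosing, or whether the footnotes are meant to bind in Part B as they do elsewhere.

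The Part C wording inherits the problem. Four weekly doses of 3 mg/kg would satisfy Section 4.3.4 but not Section 3.1.2. That condition controls escalation to 5 or 10 mg/kg in a first-in-human paediatric study, so it should have a single reading.

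**Working it through.** The plan gives no figure to reproduce here; this is interval arithmetic.

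**Inputs**
- Weekly interval: 7 days (Section 1.3 definition).
- Every-other-week interval: 14 days.
- Minimum interval: 10 days (Appendix B and C footnotes).
- Visit window: ±5 days at Part B visits, except +3 at Week 28 (Appendices B and C).
- Part B Year 1 span: Weeks 28 to 52, which is 24 × 7 = 168 days.

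**1. Nominal interval.** 7 − 10 = −3 days, so weekly dosing is 3 days short. Every-other-week dosing is 14 − 10 = 4 days clear.

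**2. Could the visit window rescue weekly dosing?** The windows are written for two-weekly visits; applying them to weekly visits is my assumption. If the first infusion is 5 days early and the last 5 days late, k consecutive intervals span at most 7k + 10 days, and they need at least 10k.

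7k + 10 ≥ 10k gives k ≤ 10/3 = 3.33.

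At most three consecutive intervals, or four infusions, could comply. A breach is unavoidable by the fifth weekly infusion.

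**3. Capacity over Weeks 28 to 52**

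| Rule | Calculation | Infusions |
|---|---|---|
| Weekly | 168/7 + 1 | 25 |
| 10-day minimum | floor(168/10) + 1 | 17 |
| 10-day minimum, Week 52 visit 5 days late | floor(173/10) + 1 | 18 |
| Every other week | 168/14 + 1 | 13 |

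The 13 matches the number of dosing columns in Appendix B. A weekly subject would therefore have 25 − 13 = 12 infusions without a column.

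**4. Part C entry condition.** Four doses contain three intervals: 3 × 7 = 21 days if weekly, 3 × 14 = 42 days if every other week. Anyone who meets the Section 3.1.2 wording also meets the dose count in Section 4.3.4. The converse fails only for a subject who received 3 mg/kg weekly.

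**The case against.** Weekly dosing is not a standing regimen. The text is "dose or dosing frequency (eg, QOW or QW) modifications may be considered by the Sponsor after consultation with the SRC", with weekly dosing given only as an example. No site can start it by reading Section 3.1.2; a Sponsor decision must come first. A reader might infer that Part B dosing automatically breaks the interval rule, or that a site following one passage necessarily violates the other. The documents do not support that. Section 1.4.1 describes Part B dosing up to 20 November 2015 as every other week, and neither document reports any weekly use.

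The footnotes might also be read as governing only the default two-weekly grid, since Section 6.1 and the synopsis leave the rule out for Part B. That reading is plausible, but nothing states it, and the footnotes are worded as mandatory. It shows that the scope is unclear; it does not remove the conflict.

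A reader might further infer that weekly infusions would go without safety data. That goes too far. Adverse events and concomitant medications are continuous in the Part B tables, Section 7.3 requires adverse events to be sought at each contact, Section 5.1.7 sets vital signs for dosing visits generally, and the Section 6.2 stopping rules cover Part B. What is missing is a schedule column. Nor does weekly dosing necessarily double the cumulative dose: that holds only if the mg/kg per infusion is unchanged, and Section 3.1.2 lets dose or frequency change.

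The consequence for analysis is also limited. Development was stopped on 11 July 2017 (SAP Section 4), and the SAP displays results by Part C dose, both every other week. Some consequence remains for any weekly infusions that did occur: dosing is listed by visit (SAP Section 7.3.1), data are tabulated by the visit recorded on the eCRF (Section 9.4.2), and protocol deviations are not analysed (Section 7.1.2). Such infusions would be hard to place or to class as compliant.

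**Conclusion.** The point holds as an internal inconsistency that takes effect only if the weekly option is used. Two stated rules on dosing interval cannot both be met under sustained weekly dosing: the shortfall is 3 days per interval, and at most 17 or 18 of the 25 weekly infusions would fit in Weeks 28 to 52. Stretching the visit windows delays the breach to the fifth infusion at the latest and does not prevent it; that step assumes the two-weekly windows carry over to weekly visits. The silence on Part B in Section 6.1 leaves the reach of the 10-day rule uncertain.

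The Part C entry wording is a secondary matter. The 21-day against 42-day contrast is hypothetical and depends on weekly dosing at 3 mg/kg. The correction is worth making because it is cheap and concerns dosing instructions for children. The documents show no effect on any reported result.

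**What to change.** Reconcile the following so that each rule has one reading:

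- **Frequency and interval in Part B:** Section 3.1.2 and the two synopsis statements on frequency, against the footnotes in Appendices B and C and the Part B paragraph of Section 6.1. State explicitly whether the 10-day minimum applies in Part B and to which regimens. Carry the result into SAP Sections 9.1.2 and 9.1.3.
- **Entry to Part C:** Section 3.1.2 and the synopsis Methodology, against Section 4.3.4 and the synopsis qualification list.

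Which frequency, interval or entry rule is right is a clinical decision, on which this review takes no position.

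The cost is a wording amendment, with ethics approval where applicable (Section 11). If the reconciled text needs a different visit pattern, a matching schedule of assessments must be added and any extra blood draws checked against the volume limits in Section 5.2.1. With the programme stopped, the remaining use is in reporting: a sentence in the clinical study report saying whether any subject was dosed weekly in Part B would settle how the infusion listings should be read.

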3.1.3 Part C (Therapy at 5 and/or 10 mg/kg)

Subjects who meet eligibility criteria for Part C (see Section 4.3.4) may begin Part C at their next scheduled visit provided that regulatory and ethics committee review and approval (where required) have been obtained for at their study site and the criteria for dosing in Section 3.1.3.1 are met. Part C is a randomized, open-label assessment of SBC-103 at doses of 5 or 10 mg/kg administered IV. Subjects will be randomized such that at least 1 subject from each cohort assigned in Part A will receive SBC-103 at 5 mg/kg and at least 1 subject from each cohort assigned in Part A will receive SBC-103 at 10 mg/kg. Thus each of the assigned dose levels from Part A will be represented in each of the 2 dose levels being studied in Part C. Treatment in Part C will continue through Week 156 of the study.

Details regarding the maximum planned dose, dose adjustments, and stopping rules in the event of poor tolerability are provided in Section 6.1 and Section 6.2.

Safety, PK and PD/efficacy assessments will be performed in all subjects as noted in the SOA for Part C, detailed in Section 14.4 (Appendix D). To minimize unnecessary risk and burden to subjects, the following study assessments in Part B may be used as baseline assessments for Part C in lieu of repeating the assessment prior to the first dose in Part C:

- An MRI performed within 8 weeks prior to Day 0 in Part C (Day 0C) may be used as the baseline assessment for Part C in lieu of performing an MRI on Day 0C.
- Neurocognition testing performed within 8 weeks prior to Day 0C may be used as the baseline assessment for Part C in lieu of performing neurocognition testing on Day 0C.
- A lumbar puncture performed within 4 weeks prior to Day 0C may be used as the baseline assessment for Part C in lieu of performing a lumbar puncture on Day 0C.

In addition, because individual subjects may reach Week 156 of the study at unique study visits in Part C, the following assessments in Part C may be used as the end-of-treatment assessment in lieu of repeating the assessment at Study Week 156:

- An MRI performed within 8 weeks prior to Study Week 156 may be used as the final assessment for Part C in lieu of performing an MRI at Study Week 156.
- Neurocognition testing performed within 8 weeks prior to Study Week 156 may be used as the final assessment for Part C in lieu of performing neurocognition testing at Study Week 156.
- A lumbar puncture performed within 4 weeks prior to Study Week 156 may be used as the final assessment for Part C in lieu of performing a lumbar puncture at Study Week 156.

These assessments are also noted on the SOA for Part C.

To provide complete safety data for SRC review (described in Section 3.1.3.1 below), the following subjects will be monitored in an in-patient setting for safety and tolerability as follows:

- The first subject to receive SBC-103 at 5 mg/kg will be monitored for at least 24 hours after administration of the first 5 mg/kg dose.
- The first subject to receive SBC-103 at 10 mg/kg will be monitored for at least 24 hours after administration of the first 10 mg/kg dose.

If a subject discontinues participation from Part C of the study, an additional follow-up phone call will be made 4 weeks after the subject's last administered dose in Part C unless the subject has a scheduled follow-up visit.

3.1.3.1 Criteria for Dosing in Part C

The first subject who is eligible to dose escalate in Part C (see Section 4.3.4) and who is randomized to receive 5 mg/kg in Part C will be the first subject dosed in Part C; in the event that >1 subject is eligible at the same time, subjects will be dosed sequentially based on subject identification number (eg, Subject [Site #]-003 would be dosed before Subject [Site #]-005). As shown in Figure 3, the decision to continue dosing this subject and to start dosing the remaining 4 subjects at 5 mg/kg will be made by the Sponsor based on SRC recommendations after review of 24-hour safety data from the first subject dosed at 5 mg/kg. The remaining subjects randomized to the 5 mg/kg dose group may be dosed in parallel providing they meet all eligibility criteria to participate in Part C.

The decision to dose the first subject at 10 mg/kg will be made by the Sponsor based on SRC recommendations after review of safety data from 1 subject who completes the first 2 doses at 5 mg/kg, and review of all available safety data from any other subjects who have received at least 1 dose of SBC-103 at 5 mg/kg (Figure 3). Similar to initiation of dosing at the 5 mg/kg dose level, the first subject to receive the 10 mg/kg dose will be the first eligible subject to dose escalate in Part C who is randomized to the 10 mg/kg group; in the event that >1 subject is eligible at the same time, subjects will be dosed sequentially based on subject identification number. The decision to dose the remaining 5 subjects at 10 mg/kg will be made by the Sponsor based on SRC recommendations after review of 24-hour safety data from the first subject dosed at 10 mg/kg. The remaining subjects randomized to the 10 mg/kg dose group may be dosed in parallel providing they meet all eligibility criteria to dose escalate in Part C.

Intra-subject dose escalation from 5 to 10 mg/kg based on all available safety, PK, and PD/efficacy data may not occur without prior written approval from the Sponsor. Dose reductions may be considered for safety and tolerability at any time in Part C.

Page 49 of 121

Figure 3: Planned Subject Treatment and Dose Escalation Schedule in Part C (Therapy at 5 and/or 10 mg/kg)

Page 50 of 121

